1. PROJECT TITLE

Mechanisms of Affective Touch in Chronic Pain

4. ESTIMATED DURATION OF THE STUDY

The proposed project will be ongoing for up to three years.

5. LAY LANGUAGE SUMMARY OR SYNOPSIS (no more than one paragraph)

The proposed study will see whether light and deep types of touch, common in massage therapies, reduce pain as much (or more) than other types of touch. We will also study whether these types of touch have different effects in people with chronic pain. Finally, we will examine psychological factors that might explain differences in touch perception in individuals with chronic pain. This research will improve our understanding of how massage therapy can benefit pain and health, and how this might differ in people who suffer from chronic pain.

6. SPECIFIC AIMS

Light stroking and deep pressure touch are engaged by many complementary health practices, most notably massage therapy. Massage therapy uses touch in a therapeutic context to achieve significant reductions in stress, pain, and depression [1]. There is little understanding, however, of the mechanisms by which specific touch components- such as light stroking and deep pressure- exert affective and analgesic benefits. The pleasantness of light stroking touch has been linked to the activation of C low-threshold mechanoreceptor (C-LTMR) fibers, unmyelinated sensory fibers that respond to slow gentle stroking of the skin and project to opioidergic brain regions including the insula and cingulate cortex. How C-LTMR stimulation gives rise to pleasant sensation is unknown, though studies of monkeys (e.g. [2]) and preliminary data from humans [3] suggest that opioids play a role. The affective sensory pathways of deep pressure touch, in contrast, are less studied. Numerous clinical studies have found that deep pressure touch is calming and is superior to light touch in massage therapy [4, 5]. In addition, analgesic benefits of both light touch and deep pressure have been demonstrated in the laboratory [6, 7]. However, there is a significant gap in our knowledge of how these pathways differ in individuals with chronic pain, and whether pleasant touch has the same level of analgesic effect. In our previous work, chronic pain patients showed reduced perception of C-LTMR-optimal touch: in striking contrast to healthy volunteers, pain patients rated slow and fast brushing as equivalent in both intensity and pleasantness [3]. This has now also been shown in patients with low back pain [8]. In addition, individuals with chronic pain show reduced ability to downregulate their pain experience through competing sensations, as demonstrated in the Conditioned Pain Modulation (CPM) paradigm. Furthermore, an emerging body of research suggests that breathing slower during nociceptive stimulation is associated with reduced pain perception [32-36]. Reduced respiration rate has been shown to support the pain-relieving effects of some mind-body therapies, including meditation [37, 38]. Although there is some evidence that pleasant touch reduces respiration rate (in infants) [39], it is currently unknown whether touch-induced reductions in respiration rate mediate the pain-relieving effects of C-LTMR optimal touch. In sum, we do not know how processing of affective touch and its analgesic benefits may differ in people with chronic pain, who frequently utilize touch-based therapies in an effort to relieve their pain. The long-term goal of this research is to elucidate the sensory-affective mechanisms of light and deep touch in health and in chronic pain, in order to advance understanding of manual therapies and their effects on pain and psychological well-being.

The proposed research is the subject of a pending R00 award and will determine whether light and deep pressure touch have comparable analgesic effects, and whether these effects differ in individuals with chronic pain conditions. It will also determine which factors predict the blunted affective touch perception observed in patients with chronic pain. The central hypothesis is that both light and deep pressure touch exert analgesic benefits, and that these analgesic effects will correlate with the pleasantness of touch. Further, we predict that the analgesic effects of pleasant touch will be reduced in patients with chronic pain, who experience reduced touch pleasantness. This research will advance our understanding of the mechanisms of massage therapy and its effect on those who suffer from chronic pain.

Aim 1 (R00): Determine why individuals with chronic pain show reduced C-LTMR-related touch pleasantness.

Hypotheses: I hypothesize that blunted pleasantness of C-LTMR and deep pressure touch in individuals with chronic pain will be predicted by psychological factors including depression and trauma history (due to the impact of these factors on the μ -opioid system, e.g. [9]).

Aim 2 (R00): Determine whether the analgesic effects of light and deep pressure touch are reduced in individuals with chronic pain, and whether analgesia correlates with pleasantness perception.

Hypotheses: I hypothesize that concurrent or recent administration of light or deep pressure pleasant touch will reduce the perceived pain of a phasic heat stimulus, and that this effect will be reduced in chronic pain patients. Further, I predict that the analgesic effect of affective touch will be correlated with the perceived pleasantness of the touch.

Sub-aim 2b: Determine whether CPM effects of pleasant touch are related to CPM effects of pain.

Hypotheses: I hypothesize that the CPM efficiency for painful and pleasant touch will not be correlated across participants, suggesting divergent mechanisms.

Sub-aim 2c: Determine whether analgesic effects of light stroking or deep pressure are mediated by reductions in respiration rate.

Hypotheses: I hypothesize that changes in respiration rate will predict the analgesic (CPM) effect for pleasant touch, suggesting central modulation of pain by pleasant affect-induced changes in respiration. In addition, I predict that there will be interindividual differences in respiration at baseline that correlate with pleasantness perception and respiratory-related pain modulations.

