(FM), a chronic pain condition, show reduced pleasantness of light stroking touch. This same effect has been shown now in patients with low back pain (LBP) [8]. However, the reasons for this reduction in pleasantness of affective touch are not known. Further, it is not known whether deep pressure touch is also less pleasant for patients with chronic pain. It is also not known whether pleasant touch has a reduced (or enhanced) analgesic benefit for patients with chronic pain. There is thus a significant gap in our understanding of the processing of pleasant touch in individuals with chronic pain. The proposed R00 research will identify factors underlying the alteration of affective touch perception observed in individuals with chronic pain. Further, it will identify whether the analgesic benefits of light gentle stroking, deep pressure, and neutral touch are the same in patients with chronic pain as in healthy adults, and whether the nonsegmental analgesic effect is related to the perception of touch pleasantness. The expected contribution of the proposed research is an understanding of the analgesic effects of light and deep pressure touch in healthy individuals and in chronic pain. This contribution will be significant because it will provide knowledge of the perceptual and analgesic effects of light and deep pressure touch (components of numerous complementary therapies) in people with and without chronic pain. This contribution will inform subsequent research on manual touch therapies by providing background information about the modulation of pain by affective touch, and differences in individuals with chronic pain. This should provide greater understanding of how complementary techniques work in chronic pain.

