Participants will be fitted with a BioNomadix RSP respiratory transducer belt and amplifier. Respiration rate will be recorded with MP160 and digitized using AcqKnowledge at rest and throughout the entire session.

We will test the analgesic effects of light slow brushing, deep pressure, and neutral touch (tapping) on induced pain using a modified affective-CPM paradigm. In this session, we will test the effect of non-painful touch stimuli on the conditioned pain stimulus, as has been conducted by [6, 7]. Both segmental (same dermatome) and nonsegmental (different dermatome) effects will be tested in order to determine whether pain inhibition is a bottom-up neural effect or an indirect affective effect.

After identifying limb locations identified as most comfortable by patients, we will perform calibration and will administer six affective-CPM blocks in an order counterbalanced across subjects: brushing, pressure, and

tapping, repeated with testing within a segment (same dermatome) and outside a segment (different dermatome).

Calibration (psychophysical testing): Session 2 calibration will be confirmed by testing the temperature rated as a 6 in Session 1 and adjusting as necessary.

Each affective-CPM block will include: phasic heat pain (baseline), heat pain with concurrent touch stimulus (test), and then test phasic heat perception once again (post-test), as follows:

Baseline: Heat will be administered using a thermode for 30s. Pain intensity ratings for the heat will be collected every 10s for a total of 3 ratings.

Test: 0-30s: rate pleasantness and intensity of the touch stimulus (brushing, pressure, or tapping). 30-60s: administer heat pain using a thermode concurrently; pain intensity rating of heat pain given every 10sec for a total of 3 ratings

Post-test: Repeat of baseline.

Between blocks the participant will rest for approximately 10-15min until sensation has dissipated to avoid habituation to test stimuli.

Session 2 will occur at the ACTRI and will take approximately 1-2 hours to complete.

Session 3: MRI Session for healthy controls (optional, offered until $N = 20$ controls have completed MRI)

A urine pregnancy (if applicable) test will be performed.

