Cold- and Affective-CPM: We will average the pain ratings from each stimulus period and compare the percent change of baseline to post-test ratings as our primary outcome measure. We will use ANOVA to compare differences between baseline and post-test between touch types, within or between dermatomes/segments, and between patients and healthy volunteers. A linear regression will be used to determine whether baseline touch pleasantness ratings significantly predict the CPM effect for each type of touch.

ASL/fMRI: Periods of baseline pain will be contrasted with periods of touch concurrent to pain (test) and following pain (post-test) in brain areas involved in pain processing. Connectivity analyses will be performed to identify the source of significantly reduced pain response in any of these areas during affective touch.

Inclusion of Women and Minorities:

Participants will include all genders and races. Based on the latest San Diego-based demographic consensus, we plan to recruit 60% White, 16% Asian, 7% Black, .5% Native American, .5% Pacific Islander, 12% Other race, 5% two or more races. We expect that 29% of our participants will be Hispanic or Latino. If necessary to obtain minority representation, under-represented racial groups will be targeted specifically for recruitment.

Rates of FM are higher in females than in males (9:1 ratio) [28], so an approximately 9:1 ratio is expected in the current study. All races and ethnicities will be invited to enroll. Expected demographics are based on the latest San Diego-area demographic census. If needed, to increase minority representation, recruitment efforts will include targeted advertising (e.g., flyers, postings, community outreach presentations) in communities with high minority populations and through community-based talks given by the PI and staff.

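### The introductory objective asks whether light and deep pressure touch have comparable analgesic effects, but the planned three-touch ANOVA for differences cannot support a positive answer

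*Combined protocol and SAP*

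**What the plan says.** The paragraph that introduces the aims in section 6 states that the research "will determine whether light and deep pressure touch have comparable analgesic effects". The formal Aim 2 hypothesis in the same section is different in kind: light or deep touch "will reduce the perceived pain of a phasic heat stimulus, and that this effect will be reduced in chronic pain patients". No numbered hypothesis says that light and deep touch are equal.

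In section 9, Session 2, the investigators "will administer six affective-CPM blocks in an order counterbalanced across subjects": three touch types, each tested within and outside the dermatome. Brushing versus pressure is therefore a within-person comparison.

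Under Data Analyses and Interpretation in section 9, the plan is to "compare the percent change of baseline to post-test ratings as our primary outcome measure". For touch types it says: "We will use ANOVA to compare differences between baseline and post-test between touch types". The same ANOVA also covers the dermatome factor and the two participant groups. The other CPM analysis reads: "A linear regression will be used to determine whether baseline touch pleasantness ratings significantly predict the CPM effect for each type of touch". That regression works within each touch type and does not compare one with another.

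No section gives a brushing-versus-pressure contrast, an equivalence margin, a confidence-interval criterion or a sample size for that comparison.

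**The concern.** A question about comparability has two informative answers: the effects differ by an amount that matters, or any difference is too small to matter. A test of no difference can deliver the first but not the second. A non-significant F may mean that the effects are close, or only that the data are too imprecise to separate them.

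The planned F also spreads over three touch types. A significant result could come from tapping alone and say nothing about brushing versus pressure.

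If nothing is fixed in advance, the plan offers no sound basis for a positive answer to the question in section 6, and the conclusion would rest on a judgement made after the data are seen. The documents give no reason to presume equality. Section 6 reports that deep pressure outperforms light touch in massage therapy. Section 9 cites effects of about d = 0.6 for brushing and d > 2 for compression; these come from separate studies, so they are not a direct contrast.

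**Working it through.** **1. The plan's own sample sizes (section 9, Sample Size Determination & Power; alpha 0.05, power 0.8).** All three reproduce with two-sided tests.
- Regression, f² = 0.15, three predictors: noncentral F with λ = 0.15 × 77 = 11.55 on 3 and 73 df gives 80.2% power at N = 77, as stated.
- Touch analgesia, d = 0.6, paired t: 80.4% power at n = 24, as stated.
- Patients versus controls, d = 0.78, two-sample t: 80.3% power at 27 per group, as stated.

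None of these addresses light versus deep touch.

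**2. The contrast that would answer the section 6 question.** For each participant, D = percent change under brushing minus percent change under pressure, each averaged over its segmental and nonsegmental block. The documents give no SD for D, so differences below are in assumed units of that SD.

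**3. How often a real difference gives a non-significant result.** Two-sided paired t at 0.05, noncentrality δ√n, where δ is the true difference in SD units. For δ = 0.2:
- N = 80: 0.2 × √80 = 1.79 against a critical value of 1.99; power 42.4%, so non-significant 57.6%.
- n = 40: 0.2 × √40 = 1.26 against 2.02; power 23.5%, so non-significant 76.5%.

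| True difference (SD of D) | Non-significant, N = 80 | Non-significant, n = 40 |
|---|---|---|
| 0.2 | 58% | 77% |
| 0.3 | 24% | 54% |
| 0.4 | 6% | 31% |
| 0.5 | 1% | 13% |

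These are for a single paired contrast, not the three-touch F.

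**4. What an interval would show.** Half-width of the 90% interval = t(0.95, n−1)/√n: 1.664/8.944 = 0.19 SD at N = 80 and 1.685/6.325 = 0.27 SD at n = 40.

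**5. What an equivalence rule would need.** Two one-sided tests at 0.05, which is the same as requiring the 90% interval to lie inside ±m. Power if the true difference is exactly zero, over a range of assumed margins:

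| m (SD of D) | N = 80 | n = 40 |
|---|---|---|
| 0.2 | 11% | 0.1% |
| 0.3 | 69% | 18% |
| 0.4 | 94% | 60% |
| 0.5 | 99.5% | 86% |

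The planned N can support a positive conclusion for some margins and not for others, so the margin has to be fixed and justified before the data are seen.

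**The case against.** The best defence is that the word in question appears once, in an introductory sentence. Aim 2 asks whether touch reduces pain, whether it does so less in chronic pain, and whether the effect tracks pleasantness. Section 7 frames the touch comparison as light and deep against neutral touch and predicts an advantage for pleasant touch. An ANOVA for differences suits those hypotheses about touch type and group. This stands, and it limits the weight of the point. It does not remove the mismatch, because the sentence states what the study will determine.

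Three stronger readings are tempting, and the documents do not support them.
- *That the sponsor plans to read a non-significant F as comparability.* No section says so. The question could also be answered with a difference, or left inconclusive. The point is only that no planned analysis supports a positive answer.
- *That sameness is asked throughout, including for fibromyalgia versus controls.* The lay summary (section 5) asks whether these touches "reduce pain as much (or more) than other types of touch", so its comparator is other touch. Section 7 asks whether benefits "are the same in patients with chronic pain as in healthy adults", which is an open question; the protocol predicts a reduction there and sizes it at d = 0.78. An equivalence analysis of the two groups is not called for.
- *That N = 80 supplies the margin.* A margin of about 0.33 SD gives 80% power at N = 80, but that is worked back from the sample size. It assumes a true difference of zero, complete data and pooled groups. Power falls to 64% if the true difference is 0.1 SD, and is 32% in one group of 40 even at a true difference of zero. Without an SD for the difference, it cannot be judged on the percent-change scale.

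**Conclusion.** The point holds in a limited form. Section 6 poses a comparability question about light and deep touch that the section 9 analysis can answer only in the negative, and the ANOVA as described does not isolate that pair. At an assumed true difference of 0.2 SD, a paired test would be non-significant about 58% of the time at N = 80 and 77% at n = 40, so non-significance would say little about comparability.

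These figures assume a single paired contrast, a two-sided 0.05 level, roughly normal differences and complete data; the SD units are an assumption. The numbered hypotheses and the sample-size basis are unaffected. The change is worth making because it is nearly free and lets the trial answer a question it sets itself.

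**What to change.** In section 9, Data Analyses and Interpretation:
- Add the within-person brushing-minus-pressure contrast in percent change, averaged over the segmental and nonsegmental blocks, with its confidence interval, for all participants and for each group.
- State that a non-significant F for touch type is not evidence of comparability.
- Allow the conclusion of comparability only if the 90% interval lies wholly within a margin that the sponsor justifies beforehand on the percent-change scale.

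If no margin can be justified, reword the section 6 sentence so that the study estimates the difference between light and deep pressure touch, and keep the contrast and its interval.

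The cost is a few sentences, one contrast and, if the comparability claim is kept, agreement on a margin. The six blocks already supply the data, so no participants, visits or procedures are added. The downside is that comparability becomes a harder claim to make.

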We will then familiarize participants with our touch tasks and collect baseline ratings. A brief training will be conducted to introduce sensations and rating scales. We will then collect several rounds of ratings of approximately 1 min each of light gentle brushing (using a soft paint brush), deep pressure (using a lymphedema compression sleeve inflated to <100mmHg or a commercially available massager), a neutral touch (tapping), and heat pain using a Medoc or Thermal QST thermode. Testing will occur on the limbs in areas identified as most comfortable by patients. Participants will be asked to rate their mood at various timepoints throughout the study.

Finally, we will conduct a classic CPM paradigm with a cold water bath where participants immerse their forearm into a 12°C refrigerated circulating water bath (e.g. NESLAB Digital One RTE 7, Thermo Scientific, Newington, NH, USA) for 60 seconds. The CPM paradigm is used to test the analgesic effects of a concurrent or recent test pain stimulus on a conditioned pain stimulus. The effects of the cold-CPM paradigm will be contrasted with a modified affective-CPM paradigm in Session 2. The cold-CPM block will include: phasic heat pain (baseline), heat pain while concurrently placing hand in the cold water bath (test), and then test phasic heat perception once again (post-test), as follows:

Calibration (psychophysical testing): determine level of heat to administer that results in a verbal pain rating of 6 out of 10 (0 = no pain; 10 = intolerable pain). An ascending series of 10s-duration heat stimuli between 39 and 50C will be administered until a stimulus is rated as a 6 out of 10. If a 6 is surpassed, stimuli will be decreased in .5C increments until the rating of 6 is achieved. Ratings will be confirmed by administering a 30s stimulus and adjusted if necessary.

Baseline: Heat will be administered using a thermode for 30s. Pain intensity ratings for the heat will be collected every 10s for a total of 3 ratings.

Test: 0-30s: rate unpleasantness and intensity of the cold water stimulus. 30-60s: administer heat pain using a thermode concurrently; pain intensity rating of heat pain given every 10sec for a total of 3 ratings

Post-test: Repeat of baseline.

Session 1 will occur at the ACTRI and will take approximately 1 hour to complete.

Session 2: Affective-CPM Paradigm

A urine pregnancy (if applicable) and opiate test will be performed.

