We expect that FM patients will show reduced pleasantness of C-LTMR-optimal touch compared to healthy individuals as found in FM patients in [3] and LBP patients in [8]. We hypothesize that current depression and trauma history will be significant predictors of blunted C-LTMR touch pleasantness. Based on an effect size F^2 of 0.15, three predictors, alpha of 0.05, and power 0.8, this study will require $N = 77$ participants. We will round up to $N = 80$ and include $N = 40$ FM patients and $N = 40$ healthy controls. Based on effect sizes observed in [3] and [8], this sample size will also be sufficient for the comparisons of pleasant touch.

Furthermore, we expect that FM patients will show reduced analgesic benefit of pleasant touch compared to healthy controls, due to reduced touch pleasantness ratings and our theorized relationship between touch pleasantness perception and analgesia, and due to reduced endogenous pain modulation evidenced in the CPM paradigm. We expect reduced analgesic effects of touch pleasantness in FM due to altered pleasant touch perception in FM (and LBP) [3, 8]. The studies showing analgesic effects of affective touch showed effect sizes of approximately $d = 0.6$ [6] and $d > 2$ (for the large compression area) [7], respectively. We would need 24 participants to demonstrate the smaller effect size in each group (alpha of 0.05, power of 0.8). No previous study has examined how pleasant touch modulates pain in chronic pain compared to healthy adults. To observe a difference in affective pain modulation between patients and healthy controls, based on the average large effect size of 0.78 seen across studies in [27] for CPM, this study would require 27 participants in each group, so the 40 participants calculated for each group will be sufficient. The MRI portion of the study will be a pilot study ($N = 20$), intended to provide preliminary data for future grant applications.

Data Analyses and Interpretation

Scores on the depression and trauma history questionnaires will be used as linear regressors to predict ratings of gentle brushing pleasantness.

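### Sub-aim 2b would read an absent cold-CPM/touch-CPM correlation as suggesting divergent mechanisms, but no analysis relates the two scores, and at N = 80 a non-significant r leaves a weak correlation open

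*Combined protocol and SAP*

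**What the plan says.** Section 6 (Specific Aims) frames Sub-aim 2b neutrally, as a question of whether the two kinds of CPM effect are related. Its hypothesis is that "CPM efficiency for painful and pleasant touch will not be correlated across participants, suggesting divergent mechanisms". So the expected result is a null, and a mechanistic reading is attached to it.

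Section 9, Session 1, says of the two paradigms only this: "The effects of the cold-CPM paradigm will be contrasted with a modified affective-CPM paradigm in Session 2". It gives no method. Section 9, Data Analyses and Interpretation, defines one score for both paradigms, since the plan will "compare the percent change of baseline to post-test ratings as our primary outcome measure". It then names two analyses: an ANOVA by touch type, segment and group, and a regression on pleasantness ("A linear regression will be used to determine whether baseline touch pleasantness ratings significantly predict the CPM effect for each type of touch"). Neither has cold-CPM on one side and touch-CPM on the other.

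Section 9, Sample Size Determination & Power, contains three sizings: "Based on an effect size F^2 of 0.15, three predictors, alpha of 0.05, and power 0.8" for the Aim 1 regression (77, rounded to 80), "We would need 24 participants to demonstrate the smaller effect size in each group" for touch analgesia, and, for the group difference in affective pain modulation, "based on the average large effect size of 0.78 seen across studies in [27] for CPM, this study would require 27 participants" per group. None concerns 2b.

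Session 2 has six touch blocks. Four use pleasant touch: brushing and pressure, each within and outside the dermatome. The two locations are kept apart "in order to determine whether pain inhibition is a bottom-up neural effect or an indirect affective effect". The plan does not say which of the four forms the pleasant-touch score for 2b.

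**The concern.** A predicted null needs a statement of what the data could have excluded. Without one, the natural route is to test r and take a non-significant result as agreeing with the hypothesis. That result is also what a weak true correlation would often produce at this sample size. Measurement error in two change scores pulls r further towards the predicted zero. The documents give no reliability, so no figure is put on that here.

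The hypothesis is also stated across participants, which pools FM patients and controls. The plan expects FM patients to show less touch analgesia and weaker endogenous pain modulation. If both scores are lower in FM, group membership alone produces some positive correlation.

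At stake is the conclusion of one sub-aim. A weak relation could be reported as divergent mechanisms, or a weakly positive pooled r could reflect only the group difference.

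**Working it through.** **Inputs.** N = 80 (40 FM, 40 controls), alpha 0.05, and the 0.78 SD group difference all come from Sample Size Determination & Power. Sidedness is not stated.

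**The plan's own figures.**
- Regression, F test with 3 and N - 4 df and noncentrality 0.15 × N: N = 77 gives power 0.802, so 77 reproduces (0.819 at N = 80).
- One-sample t test, d = 0.6: 24 two-sided, 19 one-sided.
- Two-sample t test, d = 0.78: 27 per group two-sided, 22 one-sided.

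All three reproduce. The 24 and 27 do so only as two-sided tests, so two-sided 0.05 is used below.

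**Critical correlation.** r = t / √(df + t²).
- Unadjusted, df = 78, t = 1.991: r = 1.991 / √(78 + 3.963) = 0.220.
- Adjusted for group, df = 77: 0.221.

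**What an observed r leaves open.** Fisher z, SE = 1/√(80 - 3) = 0.1140, so 1.96 × SE = 0.2234.
- r = 0: tanh(±0.2234) = -0.22 to 0.22.
- r = 0.20: atanh = 0.2027, limits tanh(-0.0206) and tanh(0.4261) = -0.02 to 0.40.
- The upper limit reaches 0.30 once the observed r is tanh(0.3095 - 0.2234) = 0.09.

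**Chance of a non-significant result.** Approximately Φ(1.96 - atanh(r)/SE), where r is the correlation between the scores as measured.

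| r | Unadjusted | Group-adjusted, SE = 1/√76 = 0.1147 |
|---|---|---|
| 0.20 | Φ(0.181) = 0.572 | 0.576 |
| 0.30 | Φ(-0.756) = 0.225 | 0.230 |
| 0.40 | Φ(-1.757) = 0.039 | 0.042 |

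**Pooling two groups.** With zero correlation within each group, equal group sizes, and group differences d1 (cold) and d2 (touch) in SD units:

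pooled r = (d1 × d2 / 4) / √[(1 + d1²/4)(1 + d2²/4)]

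The plan takes 0.78 from CPM studies and applies it to affective modulation. Here d1 = 0.78 throughout, and d2 is varied as an assumption.

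| d2 | Pooled r | Chance of significance |
|---|---|---|
| 0 | 0 | 5% |
| 0.3 | 0.0585/1.085 = 0.05 | 8% |
| 0.5 | 0.0975/1.106 = 0.09 | 12% |
| 0.78 | 0.1521/1.1521 = 0.13 | 21% |

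In simulation, the last case was significant in 21.8% of runs unadjusted and 4.9% after adjustment for group.

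**If equivalence were claimed.** Two one-sided tests, group-adjusted, true r = 0: power = 2Φ(atanh(b)/0.1147 - 1.645) - 1. The largest |r| that passes is tanh(atanh(b) - 1.645 × 0.1147). The bounds b are assumptions, because the documents give none.

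| Bound b | Power | Largest passing observed r in absolute value |
|---|---|---|
| 0.30 | 71% | 0.12 |
| 0.25 | 44% | 0.07 |
| 0.20 | 10% | 0.01 |

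**The case against.** The strongest reply is that the misuse is hypothetical. The sub-aim is put as an open question, the hypothesis only speaks of suggesting, and nothing ties 2b to a significance threshold. A reader might infer that the plan commits itself to declaring divergent mechanisms whenever p exceeds 0.05. It does not, and the 0.22 cut-off belongs to this check. What stands is that the plan offers no other route from data to conclusion, and cautious wording does not help if the result cannot separate zero from a weak correlation.

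Nor is the method wholly absent. Section 6 names a correlation and its unit, and section 9 defines the score. Missing are the analysis itself, the group term, the choice among four pleasant-touch blocks and a rule for reading a null.

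The sample is reasonably informative about larger correlations: 0.30 is missed about 22% of the time and 0.40 about 4%. A reader might infer that N = 80 says nothing about moderate correlations, but an observed r near zero does exclude 0.30.

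Pooling is a modest problem and works against the predicted null. It would not manufacture support for divergent mechanisms, and adjusting for group barely changes the miss rates.

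Finally, 2b drives no sizing and is not the primary outcome. Leaving a sub-aim unsized is ordinary practice and is not criticised here.

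**Conclusion.** The concern holds in limited form. Section 6 attaches a mechanistic reading to an absent correlation, and section 9 supplies no analysis relating the two scores. A non-significant r would be compatible with a weak correlation, and with a moderate one unless the observed r is close to zero. The pooled estimate can be inflated by group alone, by up to about 0.13 over the range examined. A clearly positive pooled r would still count against the hypothesis: at about 0.34 or more, its lower 95% limit exceeds 0.13.

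The figures assume that all 80 participants contribute both scores and that one two-sided test is made. A one-sided test would lower the threshold to 0.185. Bonferroni correction over two or four touch scores would raise it to 0.25 or 0.28. The touch-CPM group differences are assumptions.

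Two stronger conclusions are not supported. The trial is not shown to be too small, because its stated sizings reproduce and answer other questions. An equivalence test is not obligatory, because the plan supplies no bound and an estimate with its interval is enough to prevent the misreading. The change should be made before analysis; it does not touch the primary outcome.

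**What to change.** 1. In section 9, Data Analyses and Interpretation, add a partial correlation of cold-CPM with pleasant-touch CPM, adjusted for group and reported with its 95% CI.
2. Name before analysis the score that decides 2b: brushing and pressure combined or separate, and segmental or nonsegmental. Show the other estimates as supportive. If more than one score is to decide 2b, say how multiplicity is handled.
3. Reword the Sub-aim 2b hypothesis in section 6 so that a non-significant r is reported as no correlation detected, with the range of correlations the CI excludes, and not as evidence of divergent mechanisms.
4. Optional: if the sponsor wants to claim that the two are not correlated, set and justify a bound before analysis and require the 90% CI to lie inside it. The power figures above show that this is feasible only for a fairly wide bound.

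The cost is one analysis paragraph and one reworded sentence, with no new data, visits or participants. The downside is that 2b may have to be reported as inconclusive.
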